#### 4.2.3. Maintenance

Patients in CR or CRi after the reinduction cycle may continue to receive the combination CB-103 and venetoclax until disease progression or bone marrow transplantation.

Patients with PR or stable disease (SD) after the reinduction cycle may continue the treatment with the combination of CB-103 and venetoclax for a maximum of three additional cycles or until disease progression or bone marrow transplantation, whichevercomes first.

# 4.3. Duration of Treatment and End of Study

Patients will be followed-up for survival up to 2 years after they are enrolled onto the study.

Estimated Study period: Q4 2022 – Q4 2025

Collection of data will cease at the time when the last patient is removed from the study.

Patients that are removed from the study during cycle 1 for any reason other than toxicity or disease progression will be replaced.

Dose modifications/reductions are allowed in case of expected or observed unacceptable toxicity, at the discretion of treating physician or principal investigators.

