#### 9. RESPONSE DEFINITIONS

Because morphologic examination of the bone marrow during periods of hematopoietic recovery after intensive chemotherapy may be unreliable, a response will be based on blast percentage by flow cytometry. Flow cytometric assessment of response (MRD) should be performed at MDACC. Blast percentages determined by morphology can be used in cases where the sample submitted for flow cytometry evaluation is limited or hemodiluted. Patients will be considered evaluable for response if they have been administered greater than 50% of the dose of CB-103. Patients will be evaluable for safety if they have been administered 1 dose of CB-103.

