#### 11. TREATMENT DISCONTINUATION

Treatment will continue until discontinuation due to unacceptable toxicity, lack of response, relapse or progressive disease. This includes any of the following:

- Clinically significant progressive disease at any time.
- Death
- Possibility of undergoing allogeneic stem cell transplantation.
- Intercurrent illness that prevents further administration of treatment.
- Unacceptable adverse event(s), that are not manageable with dose adjustments and/or optimal medical management, or that, in the opinion of the Investigator, pose an unacceptable risk for the patient.
- Patient decision for study withdrawal.
- General or specific changes in the patient's condition that render the patient unacceptable for further treatment in the judgment of the Investigator, sponsor, or any regulatory body.

Page | 48 04/25/2024

Patients who discontinue treatment due to unacceptable toxicity, lack of response, relapse or progressive disease, or bone marrow transplantation are considered to have completed the study treatment per protocol. The patients need to complete End Of Treatment (EOT) visit.

Once a patient has discontinued the study treatment and has completed the EOT visit, the patient shall be followed-up for survival up to two years from enrollment onto the study: data on survival status and any new anti-cancer therapy may be collected by phone every 3 months for up to 2 years after study enrollment. In case of relevant related toxicities (i.e., Grade>1) occurring during survival follow-up, the relevant information will be collected every 4 weeks until resolution or stabilization of the event: information collected bytelephone contact is acceptable.

At disease progression or treatment discontinuation, the emergence of new neoplastic clones or further mutations during therapy with this combination shall be investigated by next generation sequencing (NGS) in peripheral blood mononuclear cells (PMBC) or, If available, bone marrow samples obtained from patients.

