#### 12. STATISTICAL CONSIDERATIONS

This is a phase II open-label single arm and single institution clinical trial to evaluate the efficacy and safety of CB-103 in combination with venetoclax in adolescent and adult patients with T-ALL/T-LL in first or second bone marrow recurrence refractory to initial induction therapy or refractory to at least one reinduction attempt. Up to 30 patients may be enrolled, without regard to Notch status; we anticipate that approximately 50% of these patients will be Notch positive. The primary efficacy endpoint of the study is overall response rate (ORR, including CR,CRi and PR rate) after the first two induction cycles, and the primary toxicity endpoint is the rate of toxic events, defined as a grade ≥3 non-haemtological AEs that are possibly or probably related to the study drugs (see Adverse Events (SAE) definition in section 9.2.2.1.) occurring during the 28 days of induction cycle.

We simultaneously monitor efficacy and toxicity using the Bayesian optimal phase 2 (BOP2) design [32]. Specifically, let n denote the interim sample size, and N denote the maximum sample size. Let  $Y_{eff}$  and  $Y_{tox}$  denote the binary efficacy and toxicity endpoints, with  $Y_{eff} = 1$  and  $Y_{tox} = 1$  indicating that patients experience efficacy and toxicity, respectively. We assume that the joint distribution of  $(Y_{eff}, Y_{tox})$  follows a multinomial distribution with four elementary outcomes:  $(Y_{eff}, Y_{tox}) = (1, 1), (1, 0), (0, 1)$  and (0, 0). Let  $\mathbf{p} = (P_{11}, P_{10}, P_{01}, P_{00})$  denote the probabilities of observing the four outcomes, and let  $P_{eff} = Pr(Y_{eff} = 1), P_{tox} = Pr(Y_{tox} = 1)$  and  $P_{efftox} = Pr(Y_{eff} = 1, Y_{tox} = 1)$ . When efficacy and toxicity endpoints are monitored separately, the joint distribution reduced to marginal distribution of efficacy and marginal distribution of toxicity, respectively.

The treatment is deemed unacceptable if  $p_{eff} \le 0.15$  or  $p_{tox} > 0.20$ . Thus, we will stop enrolling patients and claim that the treatment is unacceptable if

$$Pr(p_{eff} > 0.15|data) < \lambda \left(\frac{n}{N}\right)^{\alpha}$$

or

$$Pr(p_{tox} \le 0.20|data) < \lambda \left(\frac{n}{N}\right)^{\alpha/3},$$

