where  $\lambda$ =0.57 and  $\alpha$ =0.86 are design parameters optimized to maximize the study power, i.e., probability of correctly concluding an efficacious and safe **treatment as acceptable** when  $p_{eff}=0.3$ ,  $p_{tox}=0.10$  and  $p_{efftox}=0.05$ , while controlling that the probability of incorrectly claiming an inefficacious and toxic treatment, i.e., type I error, with  $p_{eff}=0.15$ ,  $p_{tox}=0.20$  and  $p_{efftox}=0.05$ , to 8.3%. Note that in the safety stopping rule, the original publication of the design used the probability cutoff  $\lambda(n/N)^{\alpha}$ , here the attenuation factor 3 is added (i.e.,  $\alpha/3$ ) to obtain stricter interim stopping boundaries to enhance safety.

This optimization is performed assuming a vague Dirichlet prior Dir(0.05,0.1,0.15,0.7) for p. The prior is chosen such that it corresponds to a prior effective sample size of 1 patient, and the prior estimates of p\_eff and p\_tox match the values specified when the treatment is unacceptable. The above decision rule leads to the following optimal stopping boundaries:

Table 18: Optimized stopping boundaries

# patients treate	d Stop if # response <=	OR # toxicity >=
10	0	3
20	2	5
30	5	6

When the total number of patients reaches the maximum sample size of 30, we conclude that the treatment is acceptable if the number of responses are greater than 5, and the number of toxicities are less than 6; otherwise we conclude that the treatment is unacceptable. The go/no-go criteria in Table 18 are non-binding.

Below (**Table 19**) are the operating characteristics of the design based on 10000 simulations using the BOP2 web application (BOP2 V1.4.10.0), which is available at http://www.trialdesign.org.

Table 19: Operating characteristics

Scenario	Pr(Eff)	Pr(Tox)	Pr(Eff & Tox)	Early Stopping (%)	Claim Acceptable (%)	Average Sample Size
1	0.30	0.2	0.05	48.77	33.34	21.7
2	0.15	0.3	0.05	89.47	1.56	14.2
3	0.30	0.1	0.05	14.26	77.76	27.6
4	0.15	0.1	0.05	51.07	20.83	22.3
5	0.30	0.2	0.10	49.39	31.94	21.6
6	0.15	0.2	0.05	71.48	8.34	18.2
7	0.20	0.1	0.05	31.75	45.19	25.1
8	0.15	0.4	0.06	97.62	0.19	11.6
9	0.40	0.1	0.06	9.74	86.76	28.3
10	0.40	0.4	0.16	96.03	0.50	12.1

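### Section 4.3 replaces dosed patients who leave in cycle 1, but the plan never says whether they stay in the ORR denominator and the Table 18 counts

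*Combined protocol and SAP*

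**What the plan says.** Section 4.3 (Duration of Treatment and End of Study) gives the replacement rule: "Patients that are removed from the study during cycle 1 for any reason other than toxicity or disease progression will be replaced". It draws no line between patients who have been dosed and those who have not.

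Section 12 sets the size and the primary efficacy endpoint. "Up to 30 patients may be enrolled, without regard to Notch status", and the endpoint is "overall response rate (ORR, including CR,CRi and PR rate) after the first two induction cycles". Table 18 is indexed by the number of patients treated (10, 20, 30). The final decision is taken "When the total number of patients reaches the maximum sample size of 30": acceptable with more than 5 responses and fewer than 6 toxicities. The closing paragraphs of Section 12 schedule safety and efficacy summaries for every 10 evaluable patients.

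Section 9 has two evaluability rules. For efficacy: "Patients will be considered evaluable for response if they have been administered greater than 50% of the dose of CB-103". For safety: "Patients will be evaluable for safety if they have been administered 1 dose of CB-103".

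Sections 4.3.3 and 11 list the reasons for stopping treatment. Besides toxicity and progression they include death, possible transplant, patient withdrawal, investigator-judged unsuitability, and "Intercurrent illness that prevents further administration of treatment".

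**The concern.** A dosed patient who dies in cycle 1 of a cause other than toxicity or progression, or who withdraws from the study, is replaced under the plain wording. Intercurrent illness and investigator-judged unsuitability may be covered too, because the text does not clearly separate leaving the study from stopping treatment.

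The plan does not say what happens to a replaced patient's data. If the patient stays in the counts, replacement can push enrolment past 30. If not, a treated patient disappears from the primary endpoint and the stopping rule. Departure in cycle 1 may be related to outcome, and the reason for it is judged by the investigator in an open-label single-arm trial. With 30 patients and a cut-off between 5 and 6 responses, one or two patients can decide the conclusion.

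**Working it through.** **Inputs from Section 12.** Table 18 boundaries: stop at ≤0 responses or ≥3 toxicities of 10, ≤2 or ≥5 of 20, ≤5 or ≥6 of 30. Design parameters λ = 0.57 and α = 0.86 (α/3 for toxicity). Prior Dir(0.05, 0.1, 0.15, 0.7), which gives Beta(0.15, 0.85) for response and Beta(0.2, 0.8) for toxicity.

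**Input not in the documents.** The share q of treated patients who are replaced. I assume 5%, 10% and 20%, all non-responders.

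**Step 1: reproduce the plan.** The posteriors and cut-offs return the Table 18 boundaries exactly. Exact multinomial enumeration over the three looks gives these chances of claiming the treatment acceptable:

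| Scenario in Table 19 | Response / toxicity / both | Plan | Exact |
|---|---|---|---|
| 6 (type I error) | 0.15 / 0.20 / 0.05 | 8.34% | 8.17% |
| 4 | 0.15 / 0.10 / 0.05 | 20.83% | 21.03% |
| 3 (alternative) | 0.30 / 0.10 / 0.05 | 77.76% | 78.46% |

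All ten scenarios agree within 1 percentage point. The design is sound as computed, provided every treated patient is counted.

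**Step 2: ORR if replaced patients are left out.** With a true ORR of 0.15 among all treated, the ORR among those kept is 0.15/(1 − q):

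- q = 5%: 0.15/0.95 = 15.8%
- q = 10%: 0.15/0.90 = 16.7%
- q = 20%: 0.15/0.80 = 18.8%

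**Step 3: chance of claiming acceptable.** The result depends on what is assumed about toxicity in replaced patients, so three versions are shown:

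- A: toxicity among those kept is unchanged, and the joint probability stays at 0.05.
- B: toxicity among those kept is unchanged, and the joint probability becomes 0.05/(1 − q).
- C: replaced patients carry no toxicity, so toxicity and the joint probability are both divided by (1 − q).

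| True toxicity | q | A | B | C |
|---|---|---|---|---|
| 0.20 (Scenario 6) | 0 | 8.2% | 8.2% | 8.2% |
| | 5% | 9.8% | 9.5% | 8.3% |
| | 10% | 11.6% | 11.1% | 8.2% |
| | 20% | 16.3% | 15.1% | 7.1% |
| 0.10 (Scenario 4) | 0 | 21.0% | 21.0% | 21.0% |
| | 5% | 24.7% | 24.5% | 23.7% |
| | 10% | 28.9% | 28.5% | 26.7% |
| | 20% | 39.2% | 38.4% | 32.7% |

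For an ineffective but tolerable treatment (Scenario 4) the chance rises in every version. At the scenario where the 8.3% is controlled, it rises in A and B but is flat or falls in C.

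**Step 4: the reported estimate.** Six responses with three replaced non-responders reads 6/30 = 20.0% (95% Agresti-Coull interval 9.1% to 37.7%) if they are left out. Among all treated it is 6/33 = 18.2% (8.2% to 34.8%).

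**The case against.** Several objections stand in whole or in part.

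- **Exclusion is not stated.** The plan says such patients are replaced, not that they leave the denominator. A reader might infer a rule that deletes failures. The documents support only silence on the denominator, which permits that outcome.
- **Leaving the study is not the same as stopping treatment.** Section 4.3 concerns removal from the study, whereas Sections 4.3.3 and 11 list reasons to stop treatment, after which patients remain in survival follow-up. On that reading only death from another cause and patient withdrawal are clear triggers. The wording is not consistent, however: Tables 9 and 13 tell the investigator to discontinue the patient from study.
- **The direction is not guaranteed.** Calling these patients mostly treatment failures has no support in the text, and a responder who leaves early for transplant could also be replaced. Lack of a documented response is likely only because assessment starts at day 28.
- **The 8.3% need not rise.** Patients removed for toxicity are never replaced, so version C is plausible, and there the error stays at about 7% to 8%.
- **The benchmark is undefined.** If the 15% refers to evaluable rather than all treated patients, the computed inflation is nil.
- **Separate response and safety sets are already stated in Section 9.** The replacement rule did not create that difference. Many early leavers would also fail the dose-based rule there, so the separate effect of Section 4.3 is uncertain.

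That the boundaries are non-binding does not answer the point, because the final ORR and its interval rest on the same undefined denominator. Event-free survival, which is calculated for all patients, does not repair the primary endpoint.

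**Conclusion.** The gap is real. Dosed patients can be replaced, their place in the primary ORR and in Table 18 is undefined, and replacement cannot be squared with 30 enrolled and 30 treated. If they are left out, the ORR is probably biased upward, by about 1 to 4 percentage points for q of 5% to 20% (0.8, 1.7 and 3.8). In the same range the chance of accepting an ineffective, tolerable treatment rises from 21.0% to between 24% and 39%.

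A reader might go further and conclude that the stated 8.3% type I error is inflated. The documents do not establish that: across the assumptions above the figure lies anywhere from 7.1% to 16.3%.

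All sizes rest on an assumed q, on replaced patients being non-responders, and on 15% being the true rate among all treated. The need for a denominator rule does not depend on those assumptions, and it cannot be settled credibly once outcomes are known.

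**What to change.** 1. **Section 4.3:** limit replacement to enrolled patients who receive no dose of study drug.
2. **Section 12:** state that every patient given at least one dose counts towards the 10, 20 and 30 of Table 18 and towards the ORR and toxicity denominators. A patient without a documented response, including death from any cause, is a non-responder.
3. **Section 9 and the reporting paragraph of Section 12:** align the more-than-50%-dose rule and the word evaluable with this by making the evaluable-set ORR a sensitivity analysis. Without this step, the new text would contradict them.
4. **If replacement of dosed patients is kept:** state that they remain in the denominators, and restate the maximum sample size.

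The cost is a few sentences in three sections. Under the first option no extra patients are needed beyond replacements for those never dosed, and the stated operating characteristics hold (exact 8.2% and 78.5%). The reported ORR may be slightly lower.

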# 4.3.1. End of 1st Cycle (induction cycle)

Patients are assessed for disease response on day 28 from the start of treatment (end of the **induction cycle**).

If the day 28 marrow is not hypocellular (cellularity  $\leq$  15%) and the patient is showing at least stabilization of the disease or a clinical benefit in the investigator's judgement, the patient may enter the **reinduction** cycle of CB-103 and venetoclax. Patients are defined to have a clinical benefit, if they are in complete remission (CR) or complete remission with incomplete blood count recovery (Cri), or have a decrease in disease burden, including peripheral blasts or bone marrow blasts that do not meet the criteria for CR or Cri, or have no evidence of progression.

If the day 28 marrow is hypocellular (cellularity  $\leq$  15%), then a repeat bone marrow biopsy is obtained between days 36 and 42 to assess response; if the repeat marrow is not hypocellular (cellularity  $\leq$  15%) and the patient is showing at least stabilization of the disease, the patient may enter the **reinduction** cycle of CB-103 and venetoclax.

Page | 13 04/25/2024

If the peripheral counts do not recover (ANC <  $1 \times 10^9$ /L or platelets count <  $60 \times 10^9$ /L) and there is evidence of residual leukemia in the bone marrow, the patient may enter the **reinduction** cycle of CB-103 and venetoclax at the discretion of the treating physician, after a minimum of 4 weeks from the start of the last cycle.

Patients who do not attain a defined clinical response after the **induction** cycle, may enter the **reinduction** cycle of CB-103 and venetoclax if there was no unacceptable toxicity.

# 4.3.2. End of 2nd Cycle (reinduction cycle)

Patients are assessed for disease response on day 56 from the start of treatment (end of the **reinduction cycle**):

- 1. If the day 56 marrow is not hypocellular (cellularity ≤ 15%) and the patient is showing a CR or a CRi, the patient is eligible for **maintenance** with CB-103 and venetoclax until disease progression or bone marrow transplant in the absence of discontinuation criteria.
- 2. If the day 56 marrow is hypocellular (cellularity ≤ 15%), then a repeat bone marrow biopsy is obtained between days 66 and 70 to assess response; if the repeat marrow is not hypocellular (cellularity ≤ 15%) and the patient is showing a CR or a CRi, the patient is eligible for maintenance with CB-103 and venetoclax until disease progression or bone marrow transplant in the absence of discontinuation criteria.
- 3. Patients with PR or stable disease (SD) after the reinduction cycle may continue the treatment with the combination of CB-103 and venetoclax for a maximum of three additional cycles or until disease progression or bone marrow transplantation, whicher comes first.
- 4. Non-responding patients, i.e patients without Cr or Cri or PR or SD after the reinduction cycle are discontinued from the treatment.

#### 4.3.3. End of Treatment

Treatment will continue until discontinuation due to unacceptable toxicity, lack of response, relapse or progressive disease. This includes any of the following:

- 1. Clinically significant progressive disease at any time.
- 2. Death
- 3. Possibility of undergoing allogeneic stem cell transplantation.
- 4. Intercurrent illness that prevents further administration of treatment.
- 5. Unacceptable adverse event(s), that are not manageable with dose adjustments and/or optimal medical management, or that, in the opinion of the Investigator, pose an unacceptable risk for the patient.
- 6. Patient decision for study withdrawal.

General or specific changes in the patient's condition that render the patient unacceptable for further treatment in the judgment of the Investigator, sponsor, or any regulatory body.

End of Treatment (EoT) visit is to be done 5 days after the last dose of any study treatment, unless the patient starts any subsequent antitumor therapy (in which case the EoT visit should be performed before the start of the new therapy, whenever possible).

# 4.3.4. Survival Follow-up

Page | 14 04/25/2024

Patients will be followed-up for survival data up to 2 years after their study enrollment: survival status and any new anti-cancer therapy may be collected by phone every 3 months.

#### **5. TREATMENTS ADMINISTERED**

**5.1. CB-103.** CB-103 is a novel First-in-Class pan-Notch Protein-Protein Interaction (PPI) inhibitor directly targeting the assembly of the Notch transcription complex located in the nucleus of tumor cells. Thereby it inhibits transcription of Notch-related target genes at the most downstream location in the cell nucleus.

The Investigational Medicinal Product (IMP) CB-103 will be provided in the form of capsules for oral treatment.

More detailed information on the oral formulation of CB-103 can be found in the Investigator's Brochure.

**5.1.1. Description.** CB-103 is produced under good manufacturing practice (GMP) conditions and analysed using state-of-the-art methods to ensure identity, purity and safety. CB-103 HCl is a white to off-white powder, soluble in water, with discrete polymorphism and a melting point around 173°C. Aqueous solubility is pH-dependent with higher values at lower pH. The active pharmaceutical substance is 6-(4-(tert-butyl) phenoxy) pyridin-3-amine hydrochloride with a molecular weight of 278.78 g/mol (hydrochloride) and 242.32 g/mol (free base). CB-103 is provided to patients as capsules or oral suspension for oral administration.

# 5.1.2. Nomenclature, structure and molecular weight.

Chemical name: 6-(4-(tert-butyl)phenoxy)pyridin-3-amine hydrochloride Laboratory code: CB-103.

Figure 3: Structure of CB-103 HCl

Molecular Formula: C15H18N2O · HCl (hydrochloride);

Molecular weight: 278,78 g/mol (CB-103 hydrochloride); 242.32 g/mol (CB-103 free base).

# **5.1.3.** Dosage and Administration.

CB-103 will be administered orally as 500 mg twice a day (BID) for 5 days on and 2 days off, which has now been declared the RP2D in adults (section 2.3.2 Clinical Studies), until disease progression per investigator's judgement, or until unmanageable drug related toxicity, or as long as the patients are continuing to derive clinical benefits (section 4.2 Treatment Plan). For patients already enrolled prior to Protocol Version 2.0, they will be reconsented and offered the increased dose if it is felt to be safe and in the patient's best interest by the treating physician, otherwise they may continue at their current dose of 500 mg daily.

Page | 15 04/25/2024

In the event of vomiting, no re-dosing will be provided. According to FDA recommendations, as for  $\geq$  12-year-old adolescent patients no weight-related clinically relevant effect on drug pharmacokinetics or safety are expected,  $\geq$  12-year-old adolescent patients enrolled in this trial may receive the same fixed daily dose as administered in adults (Clinical Growth Charts web page under National Center for Health Statistics at the Centers for Disease Control and Prevention website (https://www.cdc.gov/growthcharts/clinical\_charts.htm).

CB-103 will be provided as capsules of 100 mg each. Patients will be instructed to swallow the CB-103 capsules whole with a glass of water (approx. 200 mL) in the morning, on an empty stomach, at least one hour before taking breakfast; in the evening, within 8 to 12 hours of the first intake, at least one hour before the evening meal. Capsules should not be chewed prior to swallowing. Capsules that are broken, cracked, or otherwise damaged should not be ingested. In the exceptional case of a patient who is unable to swallow capsules, the capsules can be opened and the contents may be mixed in a spoon with a bit of yogurt or fruit puree in order to swallow and follow with a glass of approximately 200mL of water (IMP Manual).

**5.1.4. Drug Preparation, Storage and Handling.** All drug supplies should be stored in a secure, temperature-controlled area, which can be accessed only by the pharmacist, the Investigator, or another duly designated person. The investigational site will be supplied with study drug according to the site's needs. Patients should be given a sufficient supply to last until their next study visit. Detailed storage conditions will be provided on the medication label and on the Pharmacy Manual. Detail drug preparation instructions are provided in the manufacturer's full prescribing information brochure. Unused portions of the study drug will be discarded properly as per the institutional policies.

**5.1.5. Drug Accountability**. To ensure adequate records, CB-103 capsules will be accounted for as follows:

- patients have a diary where they document the number of capsules taken each day;
- patients are requested to return previously dispensed packages with the unused study drug as well as their completed patient diary to the clinic at each visit for accountability purposes even if they will not be dispensed with new medication at that visit;
- the Investigator or designee will review the patient diary at Day 1 of each cycle.

**5.2. Venetoclax. Venetoclax** is indicated for the treatment of patients with chronic lymphocytic leukemia (CLL) with 17p deletion, as detected by an FDA approved test, who have received at least one prior therapy.

Venetoclax is a selective and orally bioavailable small-molecule inhibitor of BCL-2, an antiapoptotic protein. Venetoclax helps restore the process of apoptosis by binding directly to the BCL-2 protein, displacing proapoptotic proteins like BIM, triggering mitochondrial outer membrane permeabilization and the activation of caspases. In nonclinical studies, venetoclax has demonstrated cytotoxic activity in tumor cells that overexpress BCL-2.

